3. LIST OF ABBREVIATIONS

ADE	Adverse Device Effect
AE	Adverse Event
ASADE	Anticipated Serious Adverse Device Effect
CE	Conformité Européenne (European Conformity)
CRF	Case Report Form
CRO	Contract Research Organization
CV	Curriculum Vitae
GCP	Good Clinical Practice
GP	General Practitioner
ICH	International Conference on Harmonization of Technical Requirements for Registration of Pharmaceuticals for Human Use
IEC	Independent Ethics Committee
JTIN	JuniOrtho™ Telescopic Intramedullary Nail
MDDs	Medical Device Deficiencies
MDR	Medical Device Regulation (EU 2017/745)
OT	Operative Technique
OI	Osteogenesis Imperfecta
PMCF	Post-Market Clinical Follow-up
IFU	Instruction for Use
ITT	Intention-To-Treat
PP	Per-Protocol
SAE	Serious Adverse Event
SAP	Statistical Analysis Plan
SDV	Source Data Verification
TMF	Trial Master File
ROM	Range of Motion
SOA	State-of-art
USADE	Unanticipated Serious Adverse Device Effect
WBP	Weight Bearing Protocol

4. SYNOPSIS

TITLE	A single center post-market clinical follow-up (PMCF) observational study evaluating the clinical performance and the safety profile of the JuniOrtho™ Telescopic Intramedullary Nail (JTIN) for the treatment of pediatric patients suffering from Osteogenesis Imperfecta
ACRONYM	JTIN
RATIONALE	This study has been planned as part of the Orthofix Srl post-market active surveillance plan for the collection of data on both the clinical performance and the safety profile of the JTIN. The rationale of the proposed study is to update and support the pre-market clinical evaluation of the JTIN with Real World Evidence clinical data in a real-life surgical setting, in order to confirm the benefit/risk ratio of this medical device and to keep the CE mark under Medical Device Regulation (MDR) requirements.
INVESTIGATIONAL DEVICE	JuniOrtho Telescopic Intramedullary Nail™ (JTIN). The JTIN is a self-extending intramedullary nail (telescopic rod) designed to address the specific demands of osteosynthesis in pediatric patients suffering from osteogenesis imperfect (OI). It is intended for the fixation of femoral and/or tibial fractures, osteotomies, malunions and non-unions. The design of the JTIN includes a female and a male component, which are anchored to the proximal cortex and distal epiphysis through screw-type fixation in femurs, and fixation in proximal and distal epiphysis in tibias. These two components slide from each other, allowing for extension of the JTIN as the bone structures remodel and patient growth occurs.
PROCEDURES	One selected site, experienced in the treatment of pediatric patients with OI, where the usage of JTIN is already part of the normal clinical practice, will participate in this study. Investigator will screen patients treated (or planned to be treated) with JTIN to verify inclusion and exclusion criteria, to achieve the enrollment of 25 cases. With lost to follow-up percentage estimated at 20%, this will lead to a total of 20 evaluable cases, i.e. 20 implanted JTIN (some patients may contribute for more than one implant). Patients are prospectively and retrospectively enrolled in the study: they may have undergone JTIN implantation from the 1 st of January 2022. Enrolled patients, since this study is non-interventional and observational, will follow the standard medical practice of the site: no requirements regarding the treatment of patients will be imposed on the site or Principal Investigator and the Sponsor will not in any manner influence the treatment decisions. Data of enrolled subjects will be collected for this study up to 1 year from surgery. The hospital standard care usually, but not exclusively, includes: surgery, discharge and plaster removal visits, and then 3 other follow up visits up to 1 year from surgery (see "Visits and Assessments Schedule"). Visits frequency is estimated as average of the site normal clinical practice, actual visit timing for each patient will be performed according to investigators and hospital staff evaluation. The patient data will be systematically collected by the investigator in eCRF.
PLANNED INVESTIGATION PERIOD	Preparation: 4 months for ethics committee submission preparation and approval.

	
Enrolment period: 6 months from site initiation.
 
Live phase: Total of 1,5 year (18 months), i.e. 6 months of enrollment period plus 1 year of clinical data collection until the last patient completed follow-up.
 
Final phase: 6 months including final monitoring, database closure and Statistical and Clinical Study Report writing.
								
OBJECTIVES	
Primary objective: to evaluate the safety of the JTIN, in terms of percentage of procedures with at least one serious/not serious adverse event certainly or possibly related to JTIN up to 1 year follow-up.
 
Secondary objectives: to evaluate clinical safety and performance of the JTIN, in terms of: implant survival for safety, bone union achievement and fracture-free survival for performance.
 
Exploratory objective: The Gillette Functional Assessment Questionnaire will be collected at different times to evaluate the changes after treatment.
								
TYPE OF THE INVESTIGATION	This study on JTIN device is a post-market, prospective and retrospective, observational, single-center study, namely a PMCF study. The design will contain a single arm, will be open label and will not involve randomization nor any additional procedure compared to routine practice.								
PLANNED INVESTIGATION PERIOD	
 
 First patient First visit	Q3 2023	Last patient First visit	Q3 2023	Last patient Last visit	Q4 2024	
 
	First patient First visit	Q3 2023	Last patient First visit	Q3 2023	Last patient Last visit	Q4 2024		
First patient First visit	Q3 2023	Last patient First visit	Q3 2023	Last patient Last visit	Q4 2024				
STUDY DURATION PER SUBJECT	The Study initiation for the subject is to be intended after patient's information and non-opposition (that can be also after the JTIN application surgery). The subject will be treated by the means of JTIN application and will follow standard clinical care of the selected site. If the information and non-opposition occur after the JTIN surgery, previous data will be collected retrospectively. The data from the standard care will be collected for this study up to 1 year follow-up visit.								
CENTER(S) / COUNTRY(IES)	
 
 Hospital	Country (EU)	City	Principal Investigator	
 
 1	France	Paris	[name]	
 
	Hospital	Country (EU)	City	Principal Investigator	1	France	Paris	[name]
Hospital	Country (EU)	City	Principal Investigator						
1	France	Paris	[name]						
Clinical data will be collected only on patients with a regular indication for JTIN as per IFU (no off-label use will be included). The JTIN is indicated for fractures, osteotomies, malunions and non-unions in femur and tibia in pediatric patients suffering from osteogenesis imperfecta. The JTIN is intended to be used in pediatric patients, older than 18 months.									
PATIENTS / GROUPS INCLUSION CRITERIA	
A patient will be included in the study if:
 
 • is in pediatric age (> 18 month and < 18 years) at the time of surgery; • is skeletally immature; • has a diagnosis for OI; 								

	
 has a regular indication for surgical intervention with JTIN to treat femoral and/or tibial fractures, osteotomies, malunions and non-unions; Patient and/or legal representative/guardian is duly informed and doesn't oppose to participation.
EXCLUSION CRITERIA	
A patient will not be included in the study who:
 
 has a medical condition that is a contraindication according to the manufacturer's instruction for use; has any conditions that in the Investigator's opinion may interfere with the study execution or due to which the patient should not participate for safety reasons; requires the application of, or has already in-situ concomitant devices that cannot be safely removed (except for permitted concomitant devices); is participating in other clinical trial or has taken part in any clinical study in the last 3 months with exception of analytical trials on genetics study related to OI (i.e. studies that do not include an investigational treatment for the patient such as new drugs or other medical devices); is likely to be lost to follow up, according to investigator's opinion.
CONCOMITANT MEDICATION/CON-COMITANT DEVICE	K-wires, bone graft and any other concomitant devices, e.g. bone screws, that were applied to fix any bone fragments but that were not considered critical for the maintenance of treated bone alignment, are permitted during the treatment. It is understood that any necessary medical devices applied on any other bones other than the one treated by JTIN are permitted as well.
SAFETY ENDPOINTS	
Safety endpoints: The safety profile of JTIN will be assessed by the following safety endpoints:
 
 Percentage (%) of procedures with at least one serious/not serious adverse event certainly or possibly related to JTIN up to 1 year follow-up (primary); Implant survival rate: it is the percentage of not exchanged nails up to 1 year follow-up.
EFFICACY ENDPOINTS	
Efficacy endpoints: the clinical performance of the JTIN will be assessed by the means of the:
 
 Bone union achieved; Post-treatment fracture-free survival up to 1 year follow-up;
EXPLORATORY ENDPOINT	Gillette Functional Assessment Questionnaire will be collected before the surgery and then at bone consolidation assessment and at 1 year follow-up.
CLINICAL PARAMETERS	
 Age at surgery Gender, height, weight OI classification Co-morbidities (other acquired or congenital deformities) and family diseases history Concomitant Medication, if applicable Treated Bone/s (femur / tibia) Surgery details (operation time, fluoroscopy time, device variant, other devices, complications—including blood loss) Intraoperative measures (for corrections): 
 Number of osteotomies Rotational correction Varus / valgus correction Shortening

	
• Postoperative radiographic measures to assess any deviations from intraoperative measures• ROM and WBP• Bone union assessment• Safety events (AE and MDD)
STATISTICAL METHODOLOGY FOR SAMPLE SIZE CALCULATION	A revision of the literature on the complication rates has been made. The scientific literature reports that the percentage of procedures which develop at least one serious/not serious adverse event certainly or possibly related to the procedure itself is between 9% and 60%, with a mean of 31%. Assuming a complication rate aligned or better than the mean observed in literature (31%), but also considering alignment with literature's results in terms of success rate (bone union), a sample size of 20 procedures will be sufficient to estimate the adverse event rate with 95% confidence interval of the upper limit fund in literature. Considering a drop-out or a non-evaluable rate of 20% of the procedures, a total of 25 procedures should be collected for this study.

4.1 Visits and Assessments Schedule

VISITS	PERIODS		ENROLLMENT		TREATMENT		FOLLOW-UP		
	Description	Number	Screening	Surgery	Hospital Discharge	Plaster or Immobilizer Removal	Bone consolidation assessment	2 nd Follow-up	3 rd Follow-up
Time Window	N/A			Day 0	1 week (± 2 days)	2 months (± 2 weeks)	5 months (± 2 months)	9 months (± 1 month)	1 year (± 1 month)
Information and non-opposition		X							
Inclusion / Exclusion Criteria		X							
Medical History		X							
Concomitant medication		X			X	X	X	X	X
Demographics		X							
X-ray/Fluoroscopy image		X				X	X	X	X
Clinical Examination		X				X	X	X	X
Gillette Functional Assessment Questionnaire		X							
Device application				X					
Range of motion		X				X	X	X	X
Weight bearing protocol		X				X	X	X	X
Safety Events			X		X	X	X	X	X
MDDs			X		X	X	X	X	X

Note: timelines and event frequency are estimated as average of the site normal clinical practice, actual visit/event timing for each patient will be performed according to investigators and hospital staff evaluation.

4.2 Schematic Diagram

[figure not shown]

Figure 4:1 Study schematic diagram

Note: timelines and event frequency are estimated as average of the site normal clinical practice, actual visit/event timing for each patient will be performed according to investigators and hospital staff evaluation.

5. INTRODUCTION

A manufacturer of a medical device must demonstrate that the intended purpose(s) and claim(s) made in relation to safety and performance of a medical device are achieved. As a general rule, such demonstration will require clinical data. Clinical data are relevant to the various aspects of the clinical safety and performance of the device. This may include data from prospective and retrospective clinical investigations of the concerned device as well as market experience of the same or equivalent devices and medical procedures and information from the scientific literature.

The aim of the present study is to collect post-market clinical evidence (post-market clinical follow up PMCF) on the use of the medical device JuniOrtho™ Telescopic Intramedullary Nail (JTIN).

This document is a PMCF study protocol for a human research study to be conducted according to the last update of: international standard ISO 14155, the European Community guideline on Good Clinical Practice (CPMP/ICH/135/95, ICH-E6, ICH-E11), MDR 2017/745, GDPR- 679/2016, declaration of Helsinki, local applicable regulations and any further update.

5.1 Background Information

Osteogenesis Imperfecta (OI), also called brittle bone disease, is a group of genetic disorders that affect connective tissue due to a lack of type I collagen. The classical Sillence types of OI (types I-IV) with autosomal dominant inheritance comprise about 80-85% of cases and are caused by mutations in the genes that encode type I collagen, COL1A1 and COL1A2. Osteogenesis imperfecta is a very polymorphic condition, apart from the classical autosomal dominant forms, there are also recessive forms, often severe. Forms with hypertrophic calluses (type V DA), and others associated with joint contractures (Bruck's syndrome). Currently, more than twenty affections are identified clinically and by molecular biology studies. The incidence of forms recognizable at birth is 1:10-20,000. The hallmark feature of OI is bone fragility, with susceptibility to fracture from minimal trauma, as well as bone deformity and growth deficiency. Secondary features include dentinogenesis imperfecta (DI), cardiopulmonary complications and, in adult years, hearing loss. The clinical features of OI represent a continuum ranging from perinatal lethality to individuals with severe skeletal deformities, mobility impairments, and very short stature to nearly asymptomatic individuals with a mild predisposition to fractures, normal dentition, normal stature, and normal life span. Fractures can occur in any bone but are most common in the limbs.

Management is ideally done by a multidisciplinary team including specialists in medical management of OI, clinical genetics, orthopedics, endocrinologist, rehabilitation medicine, paediatric dentistry, otology/otolaryngology, and mental health.

Intramedullary nails have an important role for bone stabilization and fracture prevention in patients with OI, who suffer from bone fragility and recurrent fractures. Long bones in the lower limbs of OI patients are especially prone to deformities that develop as a result of bone deformability or from malunion in fractures. Thus, it is important to provide structural support to the weakened bones of these patients, which is better accomplished with the use of intramedullary devices.

The objectives of long bone rodding in OI patients are to:

- Fracture treatment;
- Correct deformity;

- Improve function;
- Restore bone density through functional load bearing.

5.2 Rationale of the study

Orthofix Srl put the JTIN on the European market (2021) by the mean of a pre-market clinical evaluation made under the Medical Device Directive (MDD) requirements that was based on the analysis of the scientific literature of equivalent devices.

This study has been planned as part of the Orthofix Srl post-market active surveillance plan for the collection of data on both the clinical performance and the safety profile of the JTIN in a representative population of patients and users.

The rationale of the proposed study is to update and support the pre-market clinical evaluation of the JTIN with real-word-evidence clinical data, in order to confirm the benefit/risk ratio of this medical device and to keep the CE mark under Medical Device Regulation (MDR) requirements.

The uniqueness of the pediatric population manifests itself in specific indications for lower extremity reconstruction, due to osteogenesis imperfecta; different approach in compliance with operative and postoperative care in addition to need for adaptability to rapid growth and development. The JuniOrtho™ Telescopic Intramedullary Nail (JTIN) is an established, marketed device, commercially available and used as standard device in orthopedic surgeries.

The post-marketing, prospective study with CE-marked device JuniOrtho™ Telescopic Intramedullary Nail (JTIN) is designed for gathering real-world medical data from treatment of fractures, osteotomies/ bone deformities, malunions and non-unions in femur and tibia in pediatric patients (older than 18 months) suffering from osteogenesis imperfecta.

All data will be gathered from standard medical documentation from patients who have already been successfully treated with JTIN. Additionally, all procedures that patients underwent are justified by standard of care.

Constant identification of serious or unexpected serious risk related to the use of the device, especially in real-world experience may bring additional data, that can contribute to the safety of future patients.

In conclusion, patients will not directly benefit from the participation in this study but no additional risk related to the study participation is to be recognized.

6. STUDY OBJECTIVES

6.1 Primary Objective

The primary objective of the study is to evaluate the clinical safety profile of JTIN within the scope of its intended purpose, when used according to the manufacturer IFU on a representative population of subjects and users.

To fulfill this objective, one safety endpoint will be evaluated:

- Percentage (%) of procedures with at least one serious/not serious adverse event certainly or possibly related to JTIN up to 1 year follow-up.

The primary endpoint is used to calculate the sample size of the study.

6.2 Secondary Objectives

The secondary objective of the study is to evaluate the clinical safety and performance of JTIN by the three following endpoints, when the MD is used within the scope and according to the manufacturer IFU:

- Implant survival rate: percentage of not exchanged nails up to 1 year follow-up (safety);
- Bone union achievement (performance);
- Post-treatment fracture-free survival up to 1 year follow-up (performance)

These variables will be visually compared with data available on other devices on the market (state-of-the-art).

The sample size was calculated also to provide a significant sample for the evaluation of the following main performance endpoint: bone union achievement.

6.3 Exploratory Objectives

The Gillette Functional Assessment Questionnaire will be collected, according to hospital standard care, before the surgery Visit 0 (screening) and then at bone consolidation assessment (Visit 4) and at 1 year follow up (Visit 6), to evaluate the changes after treatment. The questionnaire is performed by the investigator the first time (i.e. before the surgery) observing the patient (in presence or eventually via telemedicine), and for the follow-up it can be performed by the investigator by telephone or by email with the parent (or legal representative).

The Gillette Functional Assessment Questionnaire is not specific developed for OI patients but it is used in the hospital because no other score is currently available specifically for OI patients. The hospital is aware that other factors for OI patient can interfere with the score.

7. STUDY DESIGN

7.1 Research Type

This is a Post Market Clinical Follow-up (PMCF) study which is prospective and retrospective, observational, single-center, not controlled.

No requirements regarding the treatment of patients will be imposed on the Site or Principal Investigator and the Sponsor will not in any manner influence the treatment decisions of Principal Investigator (i.e. non-interventional). The enrollment of patients and their treatment, including diagnostics and monitoring, will be guided solely by the principles of normal medical practice and the Principal Investigator's sole medical judgment. Site and Principal Investigator will ensure that the Device is used in accordance with normal medical practice and the instructions for use. The subjects will not undergo additional visit nor non-invasive, invasive or burdensome procedures additional to those performed under the normal clinical practice.

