7.2 Subjects and Sites Numbers

This study will be conducted only on patients with a regular indication for JTIN as per IFU (no off-label use will be included): the nail is indicated for fractures, osteotomies, malunions and non-unions in femur and tibia in pediatric patients suffering from osteogenesis imperfecta. The JTIN is intended to be used in pediatric patients, older than 18 months.

This study includes only one site (monocentric) located in Paris, France. The site was chosen for this study due to the number of subject devices already implanted, and the wideness of the indications covered by the surgeries. The site was also positively evaluated by sponsor for the appropriate qualification and competency of the investigator and of the staff, and availability of facilities and equipment.

The enrollment objective for this study is of 20 evaluable cases (i.e. procedures, see paragraph "Determination of the Sample Size"). For the purposes of this study, a case is defined as one implanted JTIN nail in one treated bone. Each case can be evaluated and recorded from implantation to the last visit for this study (see "Visits and Assessments Schedule" table and "Procedure" paragraph) or up to implant removal if this happens before the last visit. For each case one eCRF record will be created (see "Subject Identifier" paragraph).

Therefore, a single patient at the clinical site can contribute for more than one case e.g.: a patient can have several JTIN each implanted in a different bone, or can have more JTIN implanted in the same bone but at different times.

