10. STUDY PROCEDURES

10.1 Description of Procedures

Throughout the pre-study meetings, it was assessed and confirmed that the clinical data collected for the study purpose are part of the standard clinical practice for the participating investigational site. As this is an observational study, there are no change or influence on the normal clinical practice of the investigator and patients, and no interference with the local hospital standard of care guidelines and/or the internal therapeutic protocols set and established at the investigational site.

For the purpose of the study, the investigators will screen both:

- patients that have undergone JTIN implantation surgery from the 1st of January 2022
- patients that will receive JTIN implantation surgery (prospectively enrolled);

The investigators shall collect clinical data from the medical record of the subjects, concerning the screening criteria, the surgery (MD application) and 5 following visits: hospital discharge, plaster or immobilization removal, bone consolidation assessment and two follow-up visits. Data from patients' observation are gathered according to the site practice, therefore timelines and visit frequency presented in this protocol are estimated as average of the site normal clinical practice, actual visit timing for each patient will be performed according to investigators and hospital staff evaluation. The subjects will not undergo additional visit nor non-invasive, invasive or burdensome procedures additional to those performed under the normal clinical practice.

The patients' data will be systematically collected by the investigator in the eCRF provided by Sponsor.

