11.1.11 Notification deadlines

Notification to Sponsor

Serious MDDs and SAEs related to the investigational medical device and related procedure must be notified by the Investigator to the Sponsor through the appropriate form (Safety Reporting Form PO218-02) provided with the study documentation immediately, or within 2 calendar days from awareness, at the latest. This timeline applies only to prospective investigational data.

Please email the completed Safety Reporting Form Device deficiency and Compliant to Orthofix Srl at the following:

Safety Contact Information

[contact]

[contact]

Notification to Authorities

All SAEs related to an investigational procedure leading to death or imminent threat to death, a serious injury or disease, requiring a rapid corrective action must be notified by the sponsor to Competent Authority immediately or within 2 days at the latest.

Other SAEs must be notified by the sponsor to Competent Authority immediately or within 7 days at the latest.

The same guidance applies to complementary information related to these events.

In addition, as this is a PMCF observational study regarding a CE-marked device, the sponsor will comply with Articles 87 to 90 of MDR and detailed in MDCG 2023-3 (published in February 2023)

According to mentioned articles and guidelines, the sponsor will report to the competent authority all incidents that will occur during the use of the medical device covered by this study by specific reporting. For serious incidents with the most urgency, the reporting will be through Manufacturer Incident Report MIR 7.2.1 and sent to the competent authority with the most urgency and in any case no later than 10 days as well as to the local EC. For all other incidents, this timeline is within 30 days.

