23 PRIMARY OBJECTIVE

The primary objective of the study is to evaluate the clinical safety profile of JTIN within the scope of its intended purpose, when used according to the manufacturer IFU on a representative population of subjects and users.

To fulfil this objective, one safety endpoint will be evaluated:

- Percentage (%) of procedures with at least one serious/not serious adverse event certainly or possibly related to JTIN up to 1 year follow-up.**

This objective will be analysed through the descriptive analysis of the variables as detailed below:

This analysis will be performed on FAS/FAIS population.

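### Retrospective and prospective cases are pooled in the primary related-AE rate, and no planned output would show a difference in event capture between them

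*Protocol*

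**What the plan says.** - Design: protocol 7.1 describes a study "which is prospective and retrospective, observational, single-center, not controlled". The Synopsis adds "Patients are prospectively and retrospectively enrolled in the study".
- Who is screened: protocol 10.1 lists "patients that have undergone JTIN implantation surgery from the 1st of January 2022" alongside patients still to be operated on. On site selection, 7.2 states "The site was chosen for this study due to the number of subject devices already implanted".
- Mixed cases: under the Synopsis entry on duration per subject, participation starts after information and non-opposition, which may follow surgery. "If the information and non-opposition occur after the JTIN surgery, previous data will be collected retrospectively". One case can therefore hold both kinds of follow-up.
- Primary endpoint (protocol 6.1): "Percentage (%) of procedures with at least one serious/not serious adverse event certainly or possibly related to JTIN up to 1 year follow-up". Non-serious events count.
- Analysis set: SAP 13 puts every JTIN application in FAS subjects into the FAIS. SAP 23 adds "This analysis will be performed on FAS/FAIS population".
- Breakdowns: SAP 23.1 reports by patient or procedure, seriousness, relatedness and OI type. Neither document has a table, listing or sensitivity analysis by enrolment mode, and patient disposition (SAP 15.1) does not ask for one.
- AE definition (protocol 11.1.1): chronic but stable conditions diagnosed before inclusion belong to medical history, not the AE pages. Chronic diseases diagnosed during participation are AEs.
- Verification (protocol 14.2): 100% source data verification of endpoint variables.

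**The concern.** In this endpoint an event that was not recorded counts as no event, so incomplete capture can only move the rate down. There are two reasons to think capture could be lower before inclusion.

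First, those events were written up, or not, before anyone was collecting them for this study. This matters most for non-serious events, which the endpoint includes.

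Second, protocol 11.1.1 ties the medical-history rule to inclusion rather than to surgery. A stable problem that arose after the operation but before inclusion, such as stiffness or residual deformity (both listed as possible device effects in 11.1.5), could be filed as history in a retrospectively enrolled case. In a prospectively enrolled case the same problem would be an AE.

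The fracture endpoint has the same exposure, because SAP 24.3 derives it from the AE form. The study is meant to support the benefit/risk assessment, so a reader should be able to see whether the rate depends on how the case entered.

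**Working it through.** **The plan's own figure.** Protocol 12.3 says 15 procedures keep the upper 95% limit at or below 60% when the rate is 31%. With the Clopper-Pearson limit and x = 0.31n left unrounded, n = 14 gives 60.5% and n = 15 gives 59.4%, so 15 reproduces. The dropout step, 20/(1 - 0.20) = 25, also reproduces.

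**Inputs for the size of the effect**
- True rate: 31%, the literature mean in protocol 12.3.
- Capture c in retrospective relative to prospective follow-up: not in the documents; assumed 90%, 70% or 50%.
- Retrospective share f: not in the documents; derived from assumed windows. From 1 January 2022 to enrolment opening in Q3 2023 (Synopsis) is 18-21 months, followed by 6 months of enrolment. Surgeries are assumed to occur at a constant rate, with earlier cases included when enrolment opens.

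**Share by case.** 18/24 = 75% and 21/27 = 78% of cases have surgery before enrolment opens.

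**Share by follow-up.** Surgeries in the last 12 months before opening are mixed: 12/24 = 50% or 12/27 = 44%. Wholly retrospective cases are 6/24 = 25% or 9/27 = 33%. If events are spread evenly over the year, half of each mixed case's follow-up is retrospective. That gives 25% + 25% = 50%, or 33.3% + 22.2% = 55.6%.

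**Formula.** Pooled rate = 31% x [1 - f(1 - c)]. This is approximate, since it treats each affected procedure as having one event.

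| Retrospective share f | c = 90% | c = 70% | c = 50% |
|---|---|---|---|
| 50% (follow-up) | 29.5% | 26.4% | 23.3% |
| 55.6% (follow-up) | 29.3% | 25.8% | 22.4% |
| 75% (cases) | 28.7% | 24.0% | 19.4% |
| 78% (cases) | 28.6% | 23.8% | 18.9% |

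If events cluster soon after surgery, the mixed cases behave more like the lower two rows.

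**Effect on the sizing target.** At n = 20 the upper limit is at or below 60% with 7 or fewer affected procedures (7/20: 59.2%; 8/20: 63.9%). The table takes half the cases as retrospective with 70% capture.

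| True rate | Chance of 7 or fewer, full capture | Chance with the loss |
|---|---|---|
| 31% | 74% | 87% |
| 60% | 2% | 11% |

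**What a split can deliver.** With 10 cases per class, 3/10 has exact limits 6.7% to 65.2% and 2/10 has 2.5% to 55.6%. Power to distinguish 31% from 15.5% with 10 per class is about 12%; 80% power needs about 116 per class. The split is descriptive only.

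**The case against.** The strongest reply is that the documents do not show different capture. Protocol 10.1 draws data from the medical record for both modes, with no change to routine practice. Section 11.1.10 has events charted under standard practice and then entered in the eCRF, and the visit descriptions do not distinguish the modes. This stands: a difference is possible, not established.

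A reader might make four stronger inferences that the documents do not support.

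- *The pooled rate is biased down.* It could be. Neither the retrospective share nor any capture rate is given.
- *Different reporting rules prove it.* In 11.1.11, "This timeline applies only to prospective investigational data" concerns the deadline for notifying the sponsor of serious deficiencies and related SAEs. It does not cover non-serious events or decide what enters the eCRF.
- *The comparison with the literature then favours the device.* Protocol 6.2 plans a visual comparison for the secondary endpoints. For the primary rate the literature enters only the sample-size reasoning, and how the published rates were ascertained is not stated.
- *If the retrospective rate is lower, the prospective rate should be compared with the literature.* That choice depends on the data and works in one direction. With a true 31% in both groups and no capture difference, it is triggered 43% of the time with 5 prospective and 15 retrospective cases, and the expected headline rate becomes 38%. With 10 and 10 the figures are 40% and 35%.

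It is also fair that the mixed design is openly disclosed. But disclosing the design does not show whether the results differ by timing of inclusion.

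**Conclusion.** The point holds in a limited form. The pooling, the inclusion of non-serious events and the absence of any output by enrolment timing are plain in the documents. The direction of any loss is also clear, because an uncharted event counts as none and source data verification compares the eCRF only with what was charted. Whether capture differs, and by how much, cannot be known from the documents.

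Under the stated assumptions a true 31% could read as anything from about 29%, which is negligible against the interval width at n = 20, down to about 19%, which is material. The lower figure needs 50% capture over the full follow-up of 75-78% of cases, and so ignores the prospective part of mixed cases. The gap is worth closing because it is cheap to do so. It does not invalidate the primary analysis.

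**What to change.** 1. In SAP 23.1, 24.2 and 24.3, derive inclusion timing from the surgery date and the inclusion (non-opposition) date in three classes: inclusion before surgery; after surgery but within 1 year; after the 1-year follow-up was complete. A yes/no flag would put a child included a week after surgery with one whose year was already over.
2. By class, show the primary related-AE rate (serious and non-serious), bone union and fracture with Clopper-Pearson limits. Label the table descriptive and keep the pooled rate as primary, with no rule that switches the headline to one class.
3. State in protocol 11.1.1 and in the SAP that events arising after surgery count as AEs whatever the inclusion date.
4. State the ascertainment limitation in the clinical study report.

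Cost: one derived variable and extra columns in planned tables. SAP 15.3 and 15.4 already use the surgery date and an ICF signature date, taken here to be the non-opposition date, so no new data should be needed. The sample size stays at 20 evaluable and 25 enrolled procedures. The drawback is small cells with wide intervals: 1/5 is 20% with limits 0.5% to 71.6%. The SAP already accepts this by splitting the same procedures into four OI groups.
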